#### **11.1.1 Safety Analysis Set**

The Safety Analysis Set is defined as patients who received at least 1 dose of any of the study drug, cytarabine, and the anthracycline drug.

#### **11.1.2 Efficacy Analysis Set**

The Efficacy Analysis Set is defined as patients who received at least 1 dose of the study drug and who have available data of the antitumor effect assessed at least at 1 time point after the start of study treatment.

#### **11.1.3 MTD Analysis Set**

The MTD Analysis Set is defined as patients who received at least 1 dose of any of the study drug, cytarabine, and the anthracycline drug, but excludes the patients listed below.

- Patients whose DLT assessment has not been performed appropriately because some of the procedures during the DLT assessment period are missing for other reasons than adverse drug reactions (eg, worsening of the clinical condition due to progression of the primary disease, AEs that are assessed as not related to the study drug)
- Patients who have taken quizartinib for the following number of days during the DLT assessment period
  - The number of days of quizartinib administration is  $\leq 9$  for patients who have

completed remission induction therapy in Cycle 1

- The number of days of quizartinib administration is  $\leq 9$  both in Cycle 1 and Cycle 2 for patients who have proceeded to remission induction therapy in Cycle 2.

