## **5.4 Assessment of Dose-limiting Toxicity**

### **5.4.1 Definition of Dose-limiting Toxicities**

The DLT assessment period is from the start day of quizartinib administration in Cycle 1 of remission induction therapy to the preceding day of Day 1 of Cycle 1 of consolidation therapy (induction phase), and a DLT is defined as any toxicity among AEs that occur during the above period that are assessed to be “related” to quizartinib, as listed below. The severity grade will be assessed according to the Common Terminology Criteria for Adverse Events (CTCAE) v4.0 Japanese version.

- $\geq$  Grade 3 non-hematological toxicities (except for the following)
  - Alopecia, anorexia, and fatigue
  - Grade 3 queasy, vomiting, or diarrhea that has improved to  $\leq$  Grade 2 within 7 days after the onset after treatment with antiemetic or antidiarrheal drugs
  - Grade 3 mucositis that has improved to  $\leq$  Grade 2 within 7 days after the onset
  - Grade 3 infections
  - Febrile neutropenia
- Hematological toxicities that have not resolved before Day 1 of Cycle 1 of consolidation therapy, as listed below
  - Peripheral neutropenia ( $< 500/\text{mm}^3$ )
  - Thrombocytopenia resulting from bone marrow aplasia or hypoplasia ( $< 20\,000/\text{mm}^3$ )

- $\geq$  Grade 3 thrombocytopenia associated with bleeding ( $< 50\ 000/\text{mm}^3$ )
- Grade 4 thrombocytopenia requiring blood transfusion ( $< 25\ 000/\text{mm}^3$ )

If there is a day when quizartinib cannot be taken due to any toxicity during the DLT assessment period, the investigator and the sponsor will discuss and decide whether to handle the toxicity as a DLT or not.

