#### **5.4.4 Enrollment of Additional Patients**

If any of the following apply, the need to enroll additional patients at the level or not will be determined through discussion between the investigator and the sponsor. The medical expert will be consulted as needed. If enrollment of additional patients is determined, the patients meeting any of the following will be excluded from DLT assessment.

- A patient is found to be ineligible after registration.
- A patient has taken quizartinib for the following number of days during the DLT assessment period.
  - The number of days of quizartinib administration is  $\leq 9$  for patients who have completed remission induction therapy in Cycle 1
  - The number of days of quizartinib administration is  $\leq 9$  both in Cycle 1 and Cycle 2 for patients who have proceeded to remission induction therapy in Cycle 2.
- A patient takes quizartinib at a higher dose at once than the dose given at the participating level during the DLT assessment period.

- The investigator or the sponsor considers it difficult to assess DLTs in a patient because some procedures during the DLT assessment period have not been performed appropriately.
- A patient is withdrawn from the study because the patient meets the criteria specified in “5.6 Withdrawal Criteria” during the DLT assessment period (except in case the study is terminated due to DLTs).
- Enrollment of additional patients is otherwise considered necessary for safety evaluation.

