#### **9.4 Definition of Adverse Drug Reactions**

AEs that are assessed as “related” to the study drug will be handled as adverse drug reactions.

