#### **11.3.2 Safety Analysis**

Other safety analyses than DLT analyses will be performed on the Safety Analysis Set, whereas DLT analyses will be performed on the MTD Analysis Set.

AEs that occur or worsen relative to the pre-treatment state after the start of study treatment (treatment emergent AEs [TEAEs]) will be tabulated. AEs collected in the study will be coded using the Medical Dictionary for Regulatory Activities (MedDRA) terminology developed by the International Conference on Harmonisation of Technical Requirements for Registration of Pharmaceuticals for Human Use (ICH), and be

tabulated by body organ group using the MedDRA system organ class (SOC) and by AE term using preferred terms (PT).

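### The MTD Analysis Set does not require a dose of quizartinib, so it admits patients in whom no DLT can occur, and no exclusion clearly removes them

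*Combined protocol and SAP*

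**What the plan says.** Section 11.1.3 defines the MTD Analysis Set as "patients who received at least 1 dose of any of the study drug, cytarabine, and the anthracycline drug, but excludes the patients listed below". The entry condition is the same as for the Safety Analysis Set in 11.1.1. The efficacy, pharmacokinetic and pharmacodynamic sets (11.1.2, 11.1.4, 11.1.5) each require a dose of the study drug itself.

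Two exclusions follow in 11.1.3:

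- **Missing procedures.** "Patients whose DLT assessment has not been performed appropriately because some of the procedures during the DLT assessment period are missing", where the reason is something other than an adverse drug reaction. Disease progression and unrelated adverse events are the examples given.
- **Too few dosing days.** Nine or fewer days of quizartinib, worded for patients who "completed remission induction therapy in Cycle 1" and, separately, for those who went on to induction Cycle 2.

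Section 11.3.2 says what the set is for: other safety analyses use the Safety Analysis Set, "whereas DLT analyses will be performed on the MTD Analysis Set". Section 5.4.1 fixes the window: "The DLT assessment period is from the start day of quizartinib administration in Cycle 1 of remission induction therapy". By 5.3.1 that day is Day 8. A DLT must also be assessed as related to quizartinib.

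**The concern.** A DLT set should hold the patients in whom a quizartinib DLT could have been seen. The entry condition in 11.1.3 does not secure this. A patient who has chemotherapy on Days 1 to 7 and then dies, withdraws or is found ineligible meets it, yet that patient's DLT window never opens. Such a patient carries no information on quizartinib toxicity. If kept in the set, the patient enlarges the denominator and can add nothing to the numerator.

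The DLT table supports the primary objective of assessing safety and choosing a dose, and it rests on 6 to 12 patients, so one patient is visible in it. Section 11.1 has the sponsor finalise population flags after the case report forms are locked. The study is open-label, so an unclear rule would be settled with the DLT results already known.

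**Working it through.** **1. The plan's own figure.** Section 11.5 gives 6 to 12 patients. Two levels of 3 make 2 × 3 = 6, and two levels of 6 make 2 × 6 = 12. The range reproduces, and it presumes that every counted patient is evaluable.

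**2. A patient lost on Days 1 to 7, set against each rule read literally.**

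- *Entry, 11.1.3:* met, by one dose of cytarabine or anthracycline.
- *Dosing-day exclusion, 11.1.3:* not triggered. The patient neither completed Cycle 1 nor went on to Cycle 2. A patient who completes Cycle 1 with no quizartinib is caught.
- *Missing-procedures exclusion, 11.1.3:* unclear. It speaks of procedures within the DLT period, and here there was no such period. Its reason test is met: it applies where procedures are "missing for other reasons than adverse drug reactions", and under 9.4 only events assessed as related "to the study drug will be handled as adverse drug reactions". An event before the first quizartinib dose cannot qualify as one.
- *Replacement grounds, 5.4.4:* the dosing-day ground is again written "for patients who have completed remission induction therapy in Cycle 1", or for those who went on to Cycle 2. The overdose, procedure and withdrawal grounds are all tied to the DLT period. Ineligibility found after registration, and a general clause on safety evaluation, remain. Whether to replace is settled by discussion between investigator and sponsor.
- *Link between the two sections:* 11.1.3 does not import the 5.4.4 grounds. Ineligibility and overdose appear in 5.4.4 but not in 11.1.3, so a patient replaced for escalation can still be in the DLT table.

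**3. Effect on the DLT table.** Suppose six evaluable patients, one DLT, and one never-exposed patient who was replaced but stays in the set. The rate changes from 1/6 = 16.7% to 1/7 = 14.3%. With two DLTs it changes from 2/6 = 33.3% to 2/7 = 28.6%.

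**4. Effect on escalation, under a condition the plan does not state.** Tables 5.4-1 and 5.4-2 pass a level on 0 of 3, or on 1 of 3 followed by at most 2 of 6 in total. With true DLT rate p and three evaluable patients in the first cohort:

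P(pass) = (1−p)³ + 3p(1−p)² × [(1−p)³ + 3p(1−p)²]

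If one of those three was never exposed, was not replaced and was counted as having no DLT:

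P(pass) = (1−p)² + 2p(1−p) × [(1−p)³ + 3p(1−p)²]

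At p = 0.4 the bracket is 0.216 + 0.432 = 0.648. The first formula gives 0.216 + 0.432 × 0.648 = 0.496, and the second gives 0.36 + 0.48 × 0.648 = 0.671.

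| Assumed p | Three evaluable | Two evaluable, one unexposed counted as no DLT |
|---|---|---|
| 0.2 | 0.856 | 0.927 |
| 0.3 | 0.689 | 0.819 |
| 0.4 | 0.496 | 0.671 |
| 0.5 | 0.313 | 0.500 |

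The documents give no DLT rate, so p is an assumption shown over a range. Steps 3 and 4 cannot both apply to the same patient: step 3 needs the patient to have been replaced, and step 4 needs the opposite.

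**The case against.** The strongest reply is that the plan already deals with this patient.

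- The missing-procedures exclusion, read naturally, removes someone whose DLT procedures are absent because of an early loss unrelated to quizartinib. Avoiding that result requires the argument that procedures in a period that never began are not missing.
- Section 3 requires DLT status to be confirmed in at least three patients per level, and calls for further enrolment where DLT cannot be properly assessed.
- Section 5.4.2 normally assesses each patient after that patient's own DLT period.
- Section 5.4.4 lists difficulty in assessing DLTs as a ground for replacement.
- Section 11.1 lets the sponsor, with medical advice as needed, assign flags to patients whom the plan does not cover.

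Most of this stands. A reader might infer from the entry condition that a never-exposed patient counts as free of DLT and so pushes the trial towards escalation and an MTD of 40 mg. The documents do not support that. No section says such a patient is counted as free of DLT, and Section 3 points the other way. Escalation runs during the study on 5.4.2 and 5.4.4, whereas the 11.1.3 flags are set after lock, so the wording of 11.1.3 cannot change an escalation decision.

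What the reply does not remove is the gap in wording. The entry condition does not fit the purpose of the set, no exclusion names a patient who never had quizartinib, and replacement is left to discussion.

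**Conclusion.** The entry condition in 11.1.3 is wrong for a DLT set and should be changed. It admits patients who cannot have a DLT, and the exclusions remove a Day 1 to 7 loss only on a reading that the text favours but does not state.

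The size is modest. The exposure is mainly the denominator of a descriptive table: about 2 percentage points with one DLT in six (16.7% to 14.3%) and about 5 with two (33.3% to 28.6%). This assumes one such patient, replaced but kept in the set.

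The shifts in the chance of passing a level, for example from 0.496 to 0.671 at an assumed DLT rate of 0.4, do not measure the effect of 11.1.3. They apply only if such a patient were left unreplaced and counted as having no DLT, which the plan nowhere provides for.

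**What to change.** 1. In 11.1.3, replace the entry condition with receipt of at least one dose of quizartinib.
2. In 5.4.4, add never having started quizartinib as a ground for exclusion from DLT assessment and for replacement.
3. If the minimum-exposure rule is extended to patients who leave during Cycle 1, state in both 11.1.3 and 5.4.4 that any patient who had a DLT stays in the set regardless of the number of days dosed.

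The third item is a necessary safeguard. Under 5.6 a Level 1 patient with a DLT is withdrawn. If that happens within nine dosing days, the patient has not completed Cycle 1 and so escapes the dosing-day exclusion as now worded. Deleting the completion condition alone would drop that patient, and 1 of 3 could become 0 of 2, which biases the DLT rate downwards. The exception is useful even without the extension: the current dosing-day rules contain none, so a patient who completes Cycle 1 with nine or fewer days because of a DLT could already be dropped.

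The cost is a few lines of wording, repeated in any further SAP definition of the set. The planned 6 to 12 patients and the escalation tables are unchanged.

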**Table 5.4-2 Criteria for Assessing Maximum Tolerated Doses (MTDs) at Level 2**

Incidence of DLTs in the first 3 patients at Level 2, and the decision	Incidence of DLTs when 3 patients are additionally enrolled at Level 2 (a total of 6 patients), and the decision
0 of 3 patients: Terminate the study (MTD: 40 mg).	—
1 of 3 patients: Additionally enroll 3 patients at Level 2.	1 of 6 patients or 2 of 6 patients: Terminate the study (MTD: 40 mg). 3 of 6 patients or 4 of 6 patients: Terminate the study (MTD: 20 mg).
2 of 3 patients or 3 of 3 patients: Terminate the study (MTD: 20 mg).	—

If any of the criteria provided in “5.4.4 Enrollment of Additional Patients” is met at Level 1 and any patient is excluded from DLT assessment, information on AEs occurring in the concerned patient, etc. should be taken into consideration to assess whether to proceed to Level 2 or not.

Whether it is necessary or not to establish a new level, in addition to Level 1 and Level 2, will be determined through discussion between the investigator and the sponsor. The medical expert will be consulted as needed.

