### **11.1 Analysis Sets**

The sponsor will finalize the population flag of individual patients for each analysis set after CRF lock. Patients with major Good Clinical Practice (GCP) violations (eg, a violation of the informed consent procedure, a major violation of study procedures) will be excluded from all analysis sets and be assessed individually. Patients with a quizartinib dose reduction for any reason after the start of study treatment will be analyzed as patients at the dosing level at the start of study treatment.

The sponsor will also finalize the population flag of patients who are not specified in the protocol or the Statistical Analysis Plan based on the advice of the medical expert as needed.

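### The nine-day dosing rule can remove a patient from the DLT count because of the DLT itself

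*Combined protocol and SAP*

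**What the plan says.** Section 11.1.3 excludes from the MTD Analysis Set "Patients who have taken quizartinib for the following number of days during the DLT assessment period". The limits are nine or fewer days for a patient who completed induction Cycle 1, and nine or fewer in each of the two cycles for a patient who went on to Cycle 2. Section 11.3.2 makes this the only population for the DLT table: other safety analyses use the Safety Analysis Set, "whereas DLT analyses will be performed on the MTD Analysis Set". Section 11.1 adds: "The sponsor will finalize the population flag of individual patients for each analysis set after CRF lock".

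Section 5.4.4 governs the cohort decision and repeats the same limits: "A patient has taken quizartinib for the following number of days during the DLT assessment period". Whether to enrol additional patients is settled by discussion between investigator and sponsor. After that: "If enrollment of additional patients is determined, the patients meeting any of the following will be excluded from DLT assessment".

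Neither day-count bullet mentions DLTs, but the bullets around them do make allowances. In Section 11.1.3, procedures missing because of adverse drug reactions do not exclude a patient. In Section 5.4.4, the withdrawal bullet applies "during the DLT assessment period (except in case the study is terminated due to DLTs").

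Section 5.5 requires quizartinib to be held from the onset of a related Grade 3 non-hematological toxicity in induction and, at Level 2, of QTcF prolongation of Grade 3 or higher. It allows up to 28 and 14 days for recovery respectively. Section 15.3 asks for renewed consent from patients with a DLT before the drug is resumed, so such patients are expected to stay on study.

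**The concern.** An evaluability rule of this kind is meant to set aside patients with too little exposure to show toxicity. Here the toxicity can itself cut the exposure, because the protocol orders the hold. A patient held early who recovers, completes Cycle 1 and goes on to consolidation then meets the exclusion because of the event being counted.

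There are two separate consequences. Removal from the reported DLT table is automatic under Section 11.1.3. Removal from the Level 2 dose decision is only possible: it depends on a choice to enrol a replacement under Section 5.4.4. The note after Table 5.4-2 offers some protection, since for a patient excluded at Level 1 "information on AEs occurring in the concerned patient, etc. should be taken into consideration to assess whether to proceed to Level 2 or not". There is no counterpart for the Level 2 decision, which is where the MTD is set.

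Determining the dose is part of the primary objective and rests on three to six patients per level. One patient is enough to change the row of the decision table.

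**Working it through.** **The plan's own figure.** There are two levels of three patients, each expandable by three. The minimum is 3 + 3 = 6 and the maximum (3 + 3) + (3 + 3) = 12, which matches Section 11.5.

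**Which patients are caught.** Cycle 1 dosing runs from Day 8 to Day 21 (Section 5.3.1), so 21 − 8 + 1 = 14 doses. The assumption is that missed doses are not made up after Day 21; the protocol describes no make-up. With k doses taken before the hold and h days missed, the dosing days are

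D = k + max(0, 14 − k − h),

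and D ≤ 9 requires both k ≤ 9 and h ≥ 5.

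- Found pre-dose on Day 15 (k = 7), h = 5: 7 + 2 = 9, excluded.
- Found post-dose on Day 15 (k = 8), h = 5: 8 + 1 = 9, excluded.
- k = 8, h = 4: 8 + 2 = 10, kept.
- k = 8, not resumed in the window: 8, excluded.

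Section 6.2 schedules ECGs on quizartinib dosing days in Cycle 1 on Days 8, 9, 15 and 21. At the first three, at most eight doses have been taken. Section 1.3.4 gives a half-life of about 3 days, so 2^(−5/3) = 0.315 of the drug remains after five days. That makes a five-day hold plausible. It does not establish how long holds will last, because Section 5.5 ties resumption to QTcF or grade.

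**Reported table.** Dropping one DLT patient turns 1/3 into 0/2, or 2/6 (33%) into 1/5 (20%).

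**Level 2 decision if one DLT patient is replaced.** Let p be the true DLT rate (assumed; the documents give none for this regimen) and L(p) = (1−p)³ + 3p(1−p)² the chance of at most one DLT in three. Then L(0.50) = 0.500 and L(0.33) = 0.745. Chance that Table 5.4-2 yields an MTD of 40 mg:

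| First three patients | Not replaced | One DLT patient replaced | p = 0.50 | p = 0.33 |
|---|---|---|---|---|
| 2 of 3 with DLT | 0 | (1−p)·L(p) | 0 → 0.250 | 0 → 0.499 |
| 1 of 3 with DLT | L(p) | (1−p) + p·L(p) | 0.500 → 0.750 | 0.745 → 0.916 |

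**Upper bound over the whole of Level 2.** Without exclusions, P(MTD 40 mg) = (1−p)³ + 3p(1−p)²·L(p). If a share q of DLT patients were dropped, replaced and their events ignored, the counted rate would be p′ = p(1−q)/(1−pq). For p = 0.50 and q = 0.25, p′ = 0.375/0.875 = 0.429. The values of q are assumptions without a source in the documents.

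| p | q = 0 | q = 0.25 | q = 0.50 |
|---|---|---|---|
| 0.30 | 0.689 | 0.789 | 0.888 |
| 0.33 | 0.632 | 0.744 | 0.859 |
| 0.40 | 0.496 | 0.626 | 0.778 |
| 0.50 | 0.313 | 0.441 | 0.626 |

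**The case against.** The strongest reply is that few patients can be affected and that people will use judgement.

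- **Reach.** Section 5.6 withdraws Level 1 patients with a DLT, and the withdrawal bullet in Section 5.4.4 spares withdrawals due to DLTs. Related Grade 4 non-hematological toxicity and unrecovered QTcF prolongation also end participation. Hematological DLTs are judged at the start of consolidation and cause no hold. A patient given Cycle 2 is excluded only with nine or fewer days in both cycles, so a full second cycle restores evaluability. This stands: the gap mainly concerns a Level 2 patient with an early, recoverable event who stays on study.
- **Recognition of the DLT.** Section 5.4.1 says that "If there is a day when quizartinib cannot be taken due to any toxicity during the DLT assessment period", investigator and sponsor decide whether to treat the toxicity as a DLT. That settles what the event is called. It does not say that the patient remains evaluable despite the day count.
- **Discretion.** Replacement requires both parties to agree to replace a patient whose DLT they have just recognised. True, so the harm to the dose decision is possible rather than directed. Section 11.1.3, however, leaves no such choice for the table. The sponsor's latitude in Section 11.1 covers patients the protocol does not specify, and this patient is specified.
- **Visibility.** The event stays in the adverse event tables by grade and relationship, and would not be hidden in a trial of 6 to 12 patients. This also stands, but it would not be counted there as a DLT.
- **The SAP.** Section 11 defers detail to a Statistical Analysis Plan, and no separate SAP text was available for this check. An exception could sit there.

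**Conclusion.** The concern holds. As written, the day count takes a patient out of the DLT analysis because of the toxicity that analysis is meant to count. The loss from the reported table is automatic for anyone who meets the limits, and the table may then disagree with the cohort decision actually taken. The effect on the Level 2 MTD is conditional on a decision to replace the patient. Given that decision, one replacement after two DLTs in three reopens a 25% to 50% chance of declaring 40 mg where Table 5.4-2 gives none, for true rates of 50% and 33%.

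The exposure arithmetic assumes no make-up of missed doses. The DLT rates and dropped shares are illustrative, and the whole-level figures are upper bounds that apply to Level 2 only. It is unclear whether the rule reaches a patient withdrawn during Cycle 1, or what counts as completing Cycle 1 when dosing was cut short.

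**What to change.** In Sections 11.1.3 and 5.4.4, state that the exclusion for nine or fewer days applies only to patients without a DLT. A patient with a DLT then counts in numerator and denominator whatever the number of dosing days, including one who does not complete Cycle 1. This limits the day-count rule only and leaves the overdose exclusion in Section 5.3.2 as it is. Extend the sentence after Table 5.4-2 on the adverse events of excluded patients to the Level 2 MTD decision. If the SAP already contains an exception, align the protocol with it.

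Two consistency points can be settled in the same amendment. The ineligibility and overdose exclusions appear in Section 5.4.4 (overdose also in 5.3.2) but not in 11.1.3; reconcile them so that the cohort decision and the DLT table share one denominator. The hold-and-resume text for DLTs in Section 5.5 carries no level limit, while Section 5.6 withdraws Level 1 patients with a DLT. Those passages must be reconciled too, since they determine which patients the day count can reach.

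The main change costs two or three sentences in the protocol and SAP, with no extra patients or procedures. The reported DLT rate may come out slightly less favourable.

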## **5.5 Criteria for Temporary Discontinuation, Dose Reduction, and Resumption of Quizartinib**

- When the need arises to use drugs that may potentially prolong the QT/QTc interval or strong CYP3A4 inhibitors by necessity during the quizartinib treatment period: Quizartinib administration should be temporarily discontinued from the start to the end of use of the above-mentioned drugs. On the day when the quizartinib is resumed after interruption, vital sign measurement, 12-lead ECG, and laboratory tests will be performed before the start of quizartinib administration (refer to “6.2 Remission Induction Therapy” and “6.3 Consolidation Therapy”).
- When  $\geq$  Grade 3 QTcF prolongation occurs in a patient at Level 2: Quizartinib administration should be temporarily discontinued from the onset time of the above event.  
If the increase in QTcF recovers to  $\leq$  30 ms, compared with the value at registration, within 14 days after the onset, quizartinib administration will be resumed at a dose reduced to 20 mg/day.  
If the increase in QTcF does not recover to  $\leq$  30 ms, compared with the value at registration, within 14 days after the onset, the study for the relevant patient will be discontinued.  
\* If  $\geq$  Grade 3 QTcF prolongation occurs in a patient at Level 1, the study for the patient should be discontinued (refer to “5.6 Withdrawal Criteria”).
- When a DLT occurs (including cases in which it takes time to assess the causality with quizartinib, cytarabine, or the anthracycline drug but the toxicity can potentially be associated with quizartinib):  
If Grade 3 non-hematological toxicity (except QTcF prolongation) occurs during the induction phase and it is assessed to be “related” to quizartinib, quizartinib administration will be temporarily discontinued from the onset time of the event. If

the event resolves to Grade 1 within 28 days after the onset of the event and the investigator or subinvestigator decides it possible to resume quizartinib administration, quizartinib administration will be resumed.

If a Grade 4 non-hematological toxicity (except QTcF prolongation) occurs during the induction phase, the study for the relevant patient will be discontinued.

Once the dose of quizartinib is reduced, the dose should not be increased again to the original dose.

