## **5.7 Prohibited Concomitant Drugs and Therapies, Restricted Concomitant Drugs, and Drugs to Be Coadministered with Care**

Prohibited concomitant drugs and therapies:

Concomitant use of the following drugs, etc. is prohibited during the quizartinib

treatment period.

As an exception, the drugs listed in 1) and 2) may be used only when the investigator or subinvestigator considers that these drugs are medically essential to prevent or treat infection. In this case, oral treatment with quizartinib should be interrupted from the start to the end of use of the drugs listed in 1) and 2), and be resumed on the following day of the end of use of the drugs. At the time of resumption, no dose reduction of quizartinib will be necessary unless the investigator or subinvestigator considers it necessary.

- 1) Drugs that may potentially prolong the QT/QTc interval
- 2) Strong CYP3A4 inhibitors
- 3) Strong or moderate CYP3A4 inducers
- 4) Crude drugs and food products with CYP3A4-inhibiting or -inducing properties (eg, foods and beverages containing St. John's wort or grapefruit)
- 5) Anticancer treatments other than quizartinib (except hydroxycarbamide)
- 6) Investigational drugs other than quizartinib, and investigational devices
- 7) Donor lymphocytes

Restricted concomitant drugs:

The following treatments should be restricted during oral treatment with quizartinib:

- Treatment with hydroxycarbamide for control of the white blood cell count:  
Restricted to a daily dose of 2 g for up to a total of 14 days

[Drugs to be coadministered with care]

During oral treatment with quizartinib, use of substrates and inhibitors of P-glycoprotein should be avoided as far as possible.

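### The DLT evaluability rule counts quizartinib days at any dose, so a Level 2 patient reduced to 20 mg without a DLT counts by rule as DLT-free at 40 mg

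*Combined protocol and SAP*

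**What the plan says.** Two sections set the minimum exposure for DLT evaluation. Section 5.4.4 lists grounds for replacing a patient, among them "A patient has taken quizartinib for the following number of days during the DLT assessment period". Section 11.1.3 excludes from the MTD Analysis Set "Patients who have taken quizartinib for the following number of days during the DLT assessment period". In both, the test opens "The number of days of quizartinib administration is", followed by a limit of 9 or fewer. It applies to Cycle 1, or to both Cycle 1 and Cycle 2 for patients who go on to Cycle 2. The unit is days on drug.

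The only ground in 5.4.4 that refers to dose is "A patient takes quizartinib at a higher dose at once than the dose given at the participating level during the DLT assessment period". No ground refers to a lower dose.

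Section 11.1 says that patients reduced for any reason "will be analyzed as patients at the dosing level at the start of study treatment".

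A Level 2 patient can be reduced without a DLT in two ways:

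- **5.7:** on restart after a QT-prolonging drug or strong CYP3A4 inhibitor, "no dose reduction of quizartinib will be necessary unless the investigator or subinvestigator considers it necessary". No toxicity is required.
- **5.5:** after Grade 3 or higher QTcF prolongation that recovers in time, "quizartinib administration will be resumed at a dose reduced to 20 mg/day". This rule has no causality condition, whereas a DLT under 5.4.1 must be related to quizartinib.

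Table 5.4-2 sets the MTD at 40 mg on 0 of 3 DLTs, or on 1 or 2 of 6.

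**The concern.** The count at Level 2 is meant to describe tolerability at 40 mg, but nothing requires a minimum number of days at 40 mg. A patient treated mostly at 20 mg and free of DLTs carries the same weight in Table 5.4-2 as one who took the full course at 40 mg. If the DLT risk is lower at 20 mg, the error runs one way, towards passing 40 mg. Section 1.3.2 describes the QTc risk as dose-dependent.

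Determining the dose for later development is part of the primary objective, and the decision can rest on three patients. One miscounted patient is a third of that evidence.

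**Working it through.** **The plan's own figure.** The sample size is 6 to 12: 2 levels × 3 = 6 and 2 levels × 6 = 12. This reproduces. No target or assumed DLT rate is stated, so every rate below is an assumption.

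**How little 40 mg exposure passes the test**

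- Planned Cycle 1 dosing (5.3.1): Days 8 to 21, so 21 − 8 + 1 = 14 days. At 40 mg that is 560 mg; at 20 mg it is 280 mg.
- Smallest evaluable number of days: 9 + 1 = 10.
- Example A: 40 mg on Days 8–10, a QT-prolonging anti-infective on Day 11 only, then 20 mg on Days 12–21. Days: 3 + 10 = 13, so evaluable. Dose: 3 × 40 + 10 × 20 = 320 mg, or 57% of 560 mg.
- Example B: 40 mg on Day 8, interruption on Days 9–12, then 20 mg on Days 13–21. Days: 1 + 9 = 10, so evaluable. Dose: 40 + 9 × 20 = 220 mg, or 39% of 560 mg and less than a full Level 1 course.
- Cycle 2: exclusion needs 9 or fewer days in both cycles. Section 5.5 does not allow a reduced dose to be raised again. So 10 days in Cycle 2, all at 20 mg, appear to be enough even if Cycle 1 fell short.

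**Effect on the decision.** Let P0 and P1 be the probabilities of 0 and 1 DLT in the first three patients, and A the probability of at most 1 DLT in the next three. Then

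P(MTD 40 mg) = P0 + P1 × A.

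*All patients at an assumed rate of 0.40:* P0 = 0.6³ = 0.216; P1 = 3 × 0.4 × 0.6² = 0.432; A = 0.216 + 0.432 = 0.648. Result: 0.216 + 0.432 × 0.648 = 0.496.

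*One of the first three reduced, with rate 0.10:* P0 = 0.9 × 0.36 = 0.324; P1 = 0.1 × 0.36 + 0.9 × 0.48 = 0.468. Result: 0.324 + 0.468 × 0.648 = 0.627.

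*The same with rate 0.20:* P0 = 0.288; P1 = 0.072 + 0.384 = 0.456. Result: 0.288 + 0.456 × 0.648 = 0.583.

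| Assumed rate at 40 mg | No reduced patient | One, rate 0.10 | One, rate 0.20 |
|---|---|---|---|
| 0.30 | 0.689 | 0.776 | 0.732 |
| 0.40 | 0.496 | 0.627 | 0.583 |
| 0.50 | 0.312 | 0.463 | 0.425 |

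**Allowing for rarity.** Suppose each of up to six patients has a chance f of being such a case, with rates 0.40 and 0.10. The average rate is p = 0.40(1 − f) + 0.10f.

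- f = 0.05: p = 0.385; P0 = 0.2326, P1 = 0.4369, A = 0.6695. Result: 0.525.
- f = 0.10: p = 0.370; P0 = 0.2500, P1 = 0.4406, A = 0.6906. Result: 0.554.

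The rise from 0.496 is therefore about 0.03 to 0.06 before it is known whether such a patient occurs, and about 0.09 to 0.13 once one is among the first three (rate at 40 mg of 0.40).

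**The case against.** **The protocol has a way out.** A reader might infer that nothing could remove such a patient. That goes too far. The last ground in 5.4.4 is "Enrollment of additional patients is otherwise considered necessary for safety evaluation", and a patient replaced on that ground leaves the DLT assessment. All of 5.4.4 works by discussion between investigator and sponsor, including its 9-day item. This stands, but the item is not triggered by a dose reduction and 11.1.3 does not repeat it. It would be applied case by case, in an open-label cohort of three, with outcomes known. If it were used, 11.1.3 would still keep the patient in the set on which DLTs are tabulated.

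**The QTcF route is close to empty.** A reader might treat the two reduction routes as equally open. They are not. Under Table 9.3-1 an event with plausible timing that known actions of the drug can explain is related, and QTc prolongation is a known action. A related event of Grade 3 or higher is a DLT and is counted. Section 5.4.1 also calls for discussion of any day missed through toxicity. An event judged unrelated should be rare. That discussion does not reach the 5.7 route, where the interruption is for a concomitant drug.

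**The 5.7 route is narrow.** The default there is restart without reduction, and nothing in the documents suggests that reduced restarts are common. For a patient who stops after Cycle 1, more than 4 missed days already meets the exclusion. Both points stand, the second only outside Cycle 2.

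**Starting-level analysis is prespecified.** It is, and it suits the safety tables. It does not settle whether a reduced patient informs the 40 mg decision.

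**The calculation treats the reduced patient as a 20 mg patient.** Example A does include three 40 mg doses. With the half-life of about 3 days in 1.3.4, a one-compartment approximation puts exposure after three daily doses at about 1 − (1/2)^(3/3) = 50% of the 40 mg steady state, close to the 20 mg steady state. The approximation is rough, which is why the reduced patient's rate is given as a range.

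**Conclusion.** The gap is real. By rule, a DLT-free Level 2 patient treated mostly at 20 mg is evaluable and counts towards an MTD of 40 mg, and only unprompted discretion in 5.4.4 could prevent it. The direction does not depend on the figures, provided that the DLT risk is lower at 20 mg.

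The size is conditional. With assumed rates of 40% at 40 mg and 10% or 20% in the reduced patient, one such patient among the first three moves P(MTD 40 mg) from 0.50 to 0.63 or 0.58. With a 5% or 10% chance per patient and a reduced-patient rate of 10%, it moves to about 0.53 or 0.55. A reader might take the larger figures as the expected bias of the trial. The documents do not support that, because they give neither DLT rates nor the frequency of reduced restarts. The point is worth correcting because the decision rests on very few patients and the correction is cheap.

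**What to change.** In both 5.4.4 and 11.1.3:

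1. Count towards the 9-day threshold only days on which the patient took the dose of the assigned level, in Cycle 1 and in Cycle 2.
2. Add an explicit sentence that any patient with a DLT stays in the MTD Analysis Set and in Tables 5.4-1 and 5.4-2, whatever the number of days.

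The second change is essential. Section 11.1.3 has no exemption for patients with a DLT, and 5.4.4 has one only in its withdrawal item. Take a Level 2 patient with a related Grade 3 QTcF event after 5 days at 40 mg who resumes at 20 mg for 7 days. Today that is 5 + 7 = 12 days, so the DLT counts. Under the first change alone it would be 5 days, and the DLT would drop out, again in favour of 40 mg.

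The cost is one phrase and one sentence in each section. Dates and amounts of doses are already recorded (6.2). An occasional DLT-free reduced patient may need replacing through the existing 5.4.4 mechanism. Dosing, interruption and reduction rules are untouched, and this point takes no view on them.
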